6 STUDY INTERVENTION

6.1 STUDY INTERVENTIONS ADMINISTRATION

6.1.1 STUDY INTERVENTION DESCRIPTION

The 24-week intervention period captures the period of highest respiratory burden post-bronchiolitis.

Use of the HEPA units (experimental) or inactive (control) units takes place for 24 weeks beginning after a pre-intervention period approximately 2 weeks in duration (methods to be described in the MOP).

Since previous related work using a pre-/post-design has shown substantial variability in PM_{2.5} concentrations even in relatively small geographic areas, we will collect baseline PM_{2.5} to control for this potentially important source of variability in homes. For example, in a study in homes with wood stoves in the western U.S., baseline median PM_{2.5} was 17, 41, and 16 µg/m³ in filter, wood stove change out and placebo arms, respectively.⁶⁹ Preliminary results from an ongoing RCT (NCT02240069) have shown a similar pattern with median baseline PM_{2.5} ranging from 23 to 41 to 30 µg/m³ in homes assigned to different intervention arms.⁹⁶ Note we will not exclude homes based on baseline PM_{2.5} measurements because even at low levels (i.e., below U.S. National Ambient Air Quality Standards), PM_{2.5} has demonstrated adverse health effects.⁹⁷

The rationale for placing the HEPA unit in the child's sleep space is that the child will typically spend a continuous number of hours daily in this space. The rationale for a second HEPA unit in a common area of the home is to maximize exposure to the intervention.

Intervention for both experimental and control conditions:

- Use of the HEPA units (experimental) or control units takes place from weeks 3-26 (approximately) after hospital discharge to home.
- A coordinator or other qualified research team member will contact the family via video or phone to prompt them to begin using the HEPA or control units. The research team member will confirm proper installation and that the two units are functioning and provide information on the lights (e.g., sensor light) on the units.
- Both the HEPA and carbon filters will be removed from the control units, and interior contents of the unit will be masked with black cardstock or similar. The door on the unit will be taped closed to make it difficult to open the units.

Title: *The BREATHE Study: Bronchiolitis Recovery and the Use of High Efficiency Particulate Air (HEPA) Filters*

Sponsor: ISCPTN DCOC

Experimental condition, Active HEPA filtration unit use: The intervention group will use two Winix 5500-2 HEPA filtration units (Appendix A) (<https://winixamerica.com/product/5500-2/>). One will be placed in the child's sleep space and one will be placed in another common room with both units running continuously on the "high" (i.e., level 3 / second from highest) setting. Each unit is 8.2 x 15.0 x 23.6 inches, and verified for a 360 sq. foot room. If a home is too small to accommodate 2 Winix units (for example, a single room residence'), one Winix unit may be used for the study. Additional features beyond HEPA and carbon filter, include plasmawave technology to reduce volatile organic compounds and odors. The plasmawave feature will be turned off to avoid ozone production.

Control condition, Inactive filter unit use: The control group will use identical-appearing Winix 5500-2 units and similar setup procedures as described above, but with no HEPA or carbon filters.

The manufacturer indicates that HEPA filters can last up to 12 months. For this reason, the filters will not be changed during the 24-week intervention period. Changeout of filters also adds the additional risk of unintentional unmasking of the family or research team members. Ideally, the carbon filter in the HEPA unit is cleaned every 3 months. However, since reduction of pollutants (e.g., volatile organic compounds) addressed by the carbon filter are not targets of the intervention, the carbon filters will not be changed out during the 24-week study.

If a HEPA unit or control unit breaks, malfunctions, or stops working, the entire unit needs to be replaced by the study team as soon as possible (by mail, pickup, or delivery). While awaiting replacement, the family will be instructed to use the working HEPA unit in the room where the infant spends the most hours.

6.1.2 DOSING AND ADMINISTRATION

Not applicable.

6.2 PREPARATION/HANDLING/STORAGE/ACCOUNTABILITY

6.2.1 ACQUISITION AND ACCOUNTABILITY

All PurpleAir and related equipment to be used by participants in the experimental and control conditions will be stored at individual sites. Study equipment will be dispensed to participants prior to their discharge to home from their hospitalization (ideally), or if not possible by mail, or local pickup/delivery. Experimental and control filtration units and related equipment will be stored at the central site and, in most cases, be mailed directly to participants. Local sites may store filtration units if preferred and deliver them directly or by mail to participating families. Arrival of the equipment in the participants' home will be confirmed by communication (including phone, text, or email) with the family by study staff, who will also arrange a time to assist with equipment set up.

6.2.2 FORMULATION, APPEARANCE, PACKAGING, AND LABELING

The HEPA and control units are identical in appearance. They will both have a standard manufacturer appearance externally with the modifications described in Section 6.1.1.

6.2.3 PRODUCT STORAGE AND STABILITY

The HEPA/control units are prepared and stored centrally prior to dispensing to participants. PurpleAir monitors with hotspots are prepared centrally then stored by individual sites prior to dispensing to participants. Healthy Homes Toolkits will be prepared by the DCOC and then shipped in bulk to the central site prior to dispensing to participants.

6.2.4 PREPARATION

Education of parent(s)/guardian(s) of participants regarding equipment use will occur during the child's hospitalization and then remotely (video, phone, or other family-preferred communication means) post-discharge to home. All participants will receive:

- 2 HEPA or control units (unless home is small enough that only one HEPA unit is needed),
- 2 kW meters (0 kW meters if home has only two-prong outlets),
- 2 PurpleAir monitors (1 if home using only one HEPA unit) and mobile hotspot with power adapter,
- 4 power strips or similar,
- 1 tape measure,
- Basic education on strategies to improve indoor air quality, and
- 1 Healthy Homes Kit.

The local site research team will assist participants remotely with setup of all study equipment.

Study staff will ensure correct placement and setup of the PurpleAir monitors and hotspot, HEPA/control units, and kW meter following a checklist (submitted separately or will be included or referenced in MOP).

Because parent(s)/guardian(s) of participants can set up all study equipment with remote support, the study team should not need to enter any participant's home. However, to reduce barriers to participation, study staff will be permitted to assist any parent(s)/guardian(s) of participant's in their home if all remote options for technical assistance are exhausted, and it is necessary to troubleshoot problems in person.

To facilitate the inclusion of rural children, this protocol allows for providing study equipment at hospital discharge to home, mailing equipment, or locally arranged pickup/delivery, and remote study activities. There are no required in-person study visits.

6.3 MEASURES TO MINIMIZE BIAS

Randomization Scheme:

Participants (within each site) will be randomized 1:1 (stratified by site) to receive HEPA filtration (intervention group) or control filtration. Permuted block randomization with a block size of 4 or 6 participants (selected at random) will be employed. The block size and block permutation will be selected at random for each site. After selecting the block size and block permutation, a participant is assigned to the first control/intervention in the block, and the remaining slots are assigned as participants continue to randomize within the site. As randomizations continue and no more slots are available in the previously assigned block, a new block is assigned and participants are randomized accordingly.

Masking:

Families will be masked as to whether their Winix units are equipped with or without HEPA/carbon filters.

Study coordinators, investigators, and other team members who interact with participants' parent(s)/guardian(s) to obtain surveys, troubleshoot equipment setup and operation, or have other interactions will remain masked through the duration of the study for individual participants. This includes masking as to which intervention the participants receive and household air quality measurements, including the baseline measurements (separate personnel will need to be on the receiving end for air quality measurement data). This will require more than one study coordinator or additional staff/technician on the study team.

Unmasked personnel (separate coordinator, technician, or other qualified personnel) will work on the HEPA units to ensure standardized appearance with tape and active or inactive filter setup. They will not assess outcomes.

6.4 STUDY INTERVENTION COMPLIANCE

Intervention compliance will be assessed in two ways: through kW meters (see Appendix C) and caregiver-reported HEPA/control unit use.

- Families will be instructed to place kW meters on the units at the onset of installation within the home to assess usage compliance with HEPA/control units. These meters enable assessment of power consumption and estimate corresponding costs for energy usage. Increasing kWh over the course of participation will indicate HEPA/control unit use. When available, we will also quantify actual kWh usage during the intervention period by comparing observed kWh used to the usage predicted from laboratory tests. The observed kWh used will be divided by the predicted usage and this quantity multiplied by 100 to determine adherence.
- Weekly surveys will also include prompts for parent(s)/guardian(s) to report whether they used the HEPA/control unit that week and on what setting it was most commonly used.

Note that the kW meters require three-prong electrical outlets. If a home has only two-prong outlets, they will not use the kW meter. Since not all participants will have kW meters and since power interruptions will change kW meter settings, caregiver reported HEPA/control unit use on weekly surveys will be the primary measure of compliance.

6.5 CONCOMITANT THERAPY

No concomitant medications are prohibited.

6.5.1 RESCUE MEDICINE

Not applicable

7 STUDY INTERVENTION DISCONTINUATION AND PARTICIPANT DISCONTINUATION/WITHDRAWAL

7.1 DISCONTINUATION OF STUDY INTERVENTION

If the family/participant chooses not to continue the study intervention (i.e., chooses to stop using the HEPA unit/control air unit), they may choose to allow their child to remain in the study and complete the remaining study procedures as indicated by the study protocol. Participants parents/guardians will still be compensated for study activities, keep HEPA units, and receive replacement filters at the end of the study, even if they do not complete the intervention. If the study intervention is discontinued, the reason for discontinuation will be documented.

7.2 PARTICIPANT DISCONTINUATION/WITHDRAWAL FROM THE STUDY

A parent/guardian is free to withdraw (at any time) their child from participation in the study (including intervention, data collection, and assessments/surveys) without prejudice to further medical treatment (withdrawal of consent). The parent(s)/guardian(s) of the participant will be asked about the reason(s) and the presence of any AEs. The parent(s)/guardian(s) will be told they do not need to answer any questions they do not want to answer. If a parent/guardian of a participant chooses to withdraw their child from the intervention, they will be asked if they want to continue to in the study assessment procedures, including measurement of air quality, submission of symptom diaries and surveys. If parent/guardian of a participant chooses to withdraw their child from all further participation in the study, then no further study activities or data collection will take place.

Moving to a new residence is not a criterion for discontinuation unless it is no longer feasible for the parent/guardian of the participant to complete the study activities.

Title: *The BREATHE Study: Bronchiolitis Recovery and the Use of High Efficiency Particulate Air (HEPA) Filters*

Sponsor: ISCPTN DCOC

An investigator may discontinue or withdraw a participant from the study for the following reason(s): If any AE, or other medical condition or situation occurs such that continued participation in the study would not be in the best interest of the participant as determined by the site investigator and/or data safety monitoring board (DSMB) or caregiver failure to follow study instructions (e.g., failure to set up the study intervention).

The reason for participant discontinuation or withdrawal from the study will be recorded on the appropriate CRF.

Participants will not be replaced.

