4 STUDY DESIGN

4.1 OVERALL DESIGN

This is a multi-center, parallel, double-blind, randomized controlled clinical trial. Two hundred eighteen children <12 months old with their first hospitalization for bronchiolitis will be randomized 1:1 (stratified by site) to receive 24 weeks of home intervention with active HEPA filtration units to improve IAQ or to a control group without a HEPA or carbon filter inside identical-appearing units. Children will be followed for respiratory symptoms during a pre-intervention period of up to two weeks following randomization and during an intervention period of 24 weeks.

This study is designed to reduce barriers to participation for rural participants in that there will be no required study visits to a distant study site, and all study activities and data collection will be conducted remotely. Participants will be identified in hospitals in ISPCTN states, maximizing the chances that rural and medically underserved populations are represented. It is common for rural children with bronchiolitis to be transferred to tertiary care centers in urban/suburban locales, so inclusion of urban hospitals will allow for recruitment of this population.¹ It is important for rural children to be represented in a bronchiolitis study in order to increase generalizability. Rural and underserved children have a higher risk of decreased access to medical care for symptoms and illness episodes, and a higher burden of asthma.^{83,84} These families may have air pollutant exposure profiles distinct from those residing in urban areas. For example, they might experience less exposure to traffic-related pollutants but may have more wood stove use or exposure to agricultural pollutants or wildfires. With its diversity of sites, the ECHO ISPCTN is well-positioned to enroll rural children that might otherwise be excluded.

Primary Objective:

To determine if use of a HEPA filtration unit home intervention reduces the respiratory symptom burden (symptom-free days; SFD) for 24 weeks compared to the use of a control unit.

Hypothesis: Children who receive a HEPA filtration home intervention after their first hospitalization with bronchiolitis will have a greater mean number of SFDs over 24 weeks compared to children in control arm.

Secondary Objectives:

1. To test the efficacy of a HEPA filtration home intervention, relative to the control arm, on difference in number of unscheduled healthcare visits for respiratory symptoms over 24 weeks.

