9.3 POPULATIONS FOR ANALYSES

Analysis Population:

Intent-to-Treat (ITT) Population: The ITT population will include all participants who are randomized to either HEPA filtration (intervention group) or inactive filter unit (control group) (referred to as two groups in the analysis section).

Per-protocol (PP) Population: The PP population will include all participants who are randomized to either the HEPA filter (intervention group) or inactive filter (control group) and have used HEPA unit on average for both units >80% of the time.

The primary set of analyses for this study will be based on ITT population. A separate analysis will be done with the PP population.

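### Protocol 7.2 lets an investigator withdraw a randomised child from the study because the unit was not set up, and nothing says outcome surveys then continue, so symptom-free-day outcomes can go missing because of non-adherence

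*Protocol*

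**What the plan says.** **Investigator withdrawal.** Protocol 7.2: "An investigator may discontinue or withdraw a participant from the study for the following reason(s"), and one listed reason is "caregiver failure to follow study instructions (e.g., failure to set up the study intervention". What the child leaves is the study, not only the intervention. The section adds: "Participants will not be replaced". The amendment summary (V-03 to V-04) gives the reason for the clause as agreement with the consent form.

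**Families who stop the unit.** Protocol 7.1 says of such a family: "they may choose to allow their child to remain in the study and complete the remaining study procedures as indicated by the study protocol". Section 7.2 likewise says that a parent who withdraws the child from the intervention is asked about continuing assessments, including the symptom surveys.

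**End of data collection.** The only explicit statement, "then no further study activities or data collection will take place", is in 7.2 and is written for a parent who withdraws the child from all participation.

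**Timing.** Protocol 4.1: "Children will be followed for respiratory symptoms during a pre-intervention period of up to two weeks following randomization". Set-up of the filtration unit therefore follows randomisation.

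**Analysis.** Protocol 9.3: "The ITT population will include all participants who are randomized to either HEPA filtration" or the control unit, and this is the primary set. Protocol 9.3 and SAP 4.2 also define a per-protocol set based on more than 80% use. Protocol 9.4.2 imputes missing primary outcomes. SAP 6.6.1 makes complete-case analysis primary, and SAP 6.8 presents imputed results beside it.

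**The concern.** A family that starts the unit and then gives up can be followed to week 26. A family that never starts it, or otherwise fails to follow instructions, can be removed by the investigator without asking to leave. Both children were randomised, and ITT needs both outcomes. The weekly survey is remote and asks about the child's symptoms, so it does not need a running unit.

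At stake is what the primary analysis estimates. Outcomes made missing because of non-adherence leave a comparison weighted towards families who used the unit, reported under the ITT label. The per-protocol set already exists for that question. The clause is also discretionary, so practice may differ among the approximately 17 hospitals (Protocol 10.1.4).

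**Working it through.** **1. The plan's own figure.** Inputs from Protocol 9.2: difference 20 days, SD 43 days, 98 per arm, two-sample t-test. Two-sided alpha of 0.05 is from Protocol 9.4.1. Effect size d = 20/43 = 0.465. Power by the noncentral t distribution is 90.0%, as stated.

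**2. Does the SAP recover the lost outcomes?**
- SAP 6.6.1 (complete case is primary): on the usual meaning of the term, a child with no post-activation weeks drops out.
- SAP 6.8 also warns that missing values are not counted as symptom-free. On that reading, a child withdrawn part-way enters with too low a total. Neither reading recovers the outcome.
- SAP 6.8, simple weekly imputation, uses the mean of observed weeks. A child withdrawn before set-up has no intervention weeks to average.
- SAP 6.8, sources of missing symptom data, lists only caregiver failure to submit or complete surveys. Investigator withdrawal is not mentioned.

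**3. Shift in the quantity estimated.** The documents give no rate of failure to set up, so the share f is an assumption, shown over a range. Assume also that the effect is 20 days in users and zero when the unit is unused, and that non-users otherwise resemble users.

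- Followed: effect = 20 × (1 − f), with 98 per arm.
- Withdrawn: effect = 20, with 98 × (1 − f) per arm.

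| f | ITT effect if followed (days) | Power if followed | n per arm if withdrawn | Power if withdrawn |
|---|---|---|---|---|
| 2% | 19.6 | 88.8% | 96.0 | 89.4% |
| 5% | 19.0 | 86.8% | 93.1 | 88.4% |
| 10% | 18.0 | 83.0% | 88.2 | 86.7% |
| 15% | 17.0 | 78.6% | 83.3 | 84.7% |

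Power is by noncentral t, SD 43, two-sided 0.05.

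Worked case, 11 of 196 non-users (5.6%):
- Withdrawn: n = 185 (92.5 per arm), effect 20 days, power 88.2%.
- Followed: effect = 20 × 185/196 = 18.9 days, 98 per arm, power 86.4%.

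Withdrawal therefore overstates the all-randomised effect by about 1.1 days in this case. It does not cost power relative to keeping the children.

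**4. Endpoint clock.** Protocol 9.1 and SAP 3.5 count the 24 weeks from activation of filtration. A child whose unit is never set up has no activation date, so continued surveys alone would not yield the primary endpoint.

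**The case against.** **The two sections address different behaviour.** Section 7.1 covers stopping, and the example in 7.2 is never starting. This stands: the gap covers non-starters and other failures to follow instructions, not families who choose to stop.

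**The end of follow-up is inferred.** The clause is permissive, and the sentence ending data collection concerns parental withdrawal. The consent pages and the manual of procedures were not available. This also stands, but the clause speaks of withdrawal from the study and nothing states that surveys go on.

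**ITT is not formally breached.** Correct. The children stay in the set, and imputed results are reported. The problem is avoidable missing data, which the complete-case primary analysis does not repair.

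**A reader might infer lost power.** The fall from 90.0% to 88.2% with 11 children withdrawn compares with a trial in which all of them benefit fully. If unused units do nothing, keeping the children gives 86.4%. Nor do the documents say these withdrawals would be additional to planned attrition: the amendment that added the clause also raised the attrition allowance from 10% to 16%.

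**A reader might infer bias between arms.** If only one arm lost 10%, and those children had 20 fewer symptom-free days, the bias under the null would be 0.10 × 20 = 2.0 days and type I error about 6.2%. That requires one-sided loss. Families and participant-facing staff are masked and the units look identical (Protocol 6.2.2, 6.3), so imbalance from failure to set up is unlikely. Later non-adherence is less protected, since families are told about the sensor light (Protocol 6.1.1) and the survey asks about a red glow (SAP 3.7). That is a possibility, not something the documents show.

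**Conclusion.** The concern holds as a gap in outcome follow-up. Section 7.2 permits withdrawal of randomised children for non-adherence and is silent on whether surveys continue, while the protocol offers continued follow-up to families who stop the unit. The consequence is missing primary outcomes selected on adherence, and a complete-case estimate that moves towards the effect in users.

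Its size cannot be fixed from the documents. Under the assumptions above, the gap between the user effect and the all-randomised effect is 0.4 days at 2% non-use, 1.0 at 5% and 2.0 at 10%. Non-users whose symptoms differ from users' would change these figures in a direction that cannot be stated. Neither a power loss nor a between-arm bias is established. The lower power from keeping these children is an acceptable cost of a true ITT estimate. The change is worth making because it is cheap and the missing data are avoidable.

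**What to change.** 1. Reconcile Protocol 7.1 and 7.2. Record failure to set up, or to follow instructions, as intervention not started or discontinued. State that weekly surveys and the week-26 questionnaire continue unless the parent withdraws consent.
2. Align the consent text at the same amendment.
3. In the SAP, define the start of the 24-week endpoint for a randomised child with no activation date. One option is the planned intervention start in the Schedule of Activities, day 14 counting discharge as day 1. State that such children enter the ITT analysis on that basis.
4. Add investigator withdrawal to the sources of missing data in SAP 6.8, and report its frequency by arm and site.

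The cost is wording in the protocol, consent form and SAP, plus survey compensation for retained families ($20 per weekly survey, Protocol 5.5). The surveys are already scheduled and remote. None of this bears on when the intervention itself should stop.
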